3.2. STUDY ENDPOINTS

1. In vitro study: The rate of diffusion from the poloxamer gel into saline will be measured at separate time intervals in order to determine the liberation of drug from the poloxamer gel.
2. In vivo study:
 1. Establish the safety of the adenosine ligands topically in the middle ear. This will be through serial measurement of plasma concentrations and systemic (cardiovascular) effects
 2. Establish a middle ear delivery system of the adenosine ligands which is consistent

4. IN-VITRO STUDY PROCEDURE

4.1. DRUG PREPARATION

4.1.1. The therapeutic agents will be sourced from their manufacturers: Istradefylline (Sigma), Poloxamer-407 gel (Sigma) and Regadenoson (Sapphire Bioscience). A formulating pharmacist will make up the following. Based on prior animal studies, the gels will be prepared at 17% w/w in cold distilled water. Istradefylline 1 mM stock solution will be prepared in 40-50% Dimethyl Sulfoxide (DMSO) and then diluted down to 200 nM. Regadenoson will be similarly prepared with 2.5 mg of drug dissolved in 2 ml DMSO before being diluted to 1:100 to give a 1% DMSO concentration. The drug solutions will then be mixed with the 17% w/w poloxamer and placed on ice until fully dissolved. To model liberation of the drug from the gel in the approximately 1 mL volume of the human middle ear, 1 mL of thermoreversible gel will be warmed to body temperature (37 degrees Celsius)

4.2. ESTABLISHING RATE OF LIBERATION OF THE DRUG FROM GEL

4.2.1. One (1)ml of the warmed drug will be placed in an Eppendorf tube. 100 micro litres of saline will be placed on it and the Eppendorf tube placed in a 37 degree water bath. At 30 minutes, 2 hours, 4 hours and 1 week 20 microlitres of saline will be removed by micropipette and sent for analysis using the liquid chromatography - tandem mass spectrometry detection method. After each 20 micro litre aliquot is removed it will be replaced by the same amount of saline to ensure the same concentrations.

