6. STATISTICAL METHODS

6.1. DETERMINATION OF SAMPLE SIZE

This exploratory study will be used to assess data variability and allow power calculations in future studies.

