6.2. STATISTICAL AND ANALYTICAL PLANS

In general, data will be summarized using descriptive statistics (mean, median, standard deviation, minimum and maximum) or frequency counts and percentages, as appropriate to the type of data.

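### In-vitro release test: refilling with saline keeps the volume constant but cuts the concentration by 20% each time, so the reason given in Protocol 4.2 is wrong and later readings understate release if taken as undisturbed

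*Protocol*

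**What the plan says.** Section 4.2 of the Protocol describes the release test. "One (1)ml of the warmed drug will be placed in an Eppendorf tube", then "100 micro litres of saline will be placed on it and the Eppendorf tube placed in a 37 degree water bath". Sampling follows: "At 30 minutes, 2 hours, 4 hours and 1 week 20 microlitres of saline will be removed by micropipette". The refill and its purpose are given in one sentence: "After each 20 micro litre aliquot is removed it will be replaced by the same amount of saline to ensure the same concentrations".

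These samples serve the in-vitro endpoint in section 3.2: "The rate of diffusion from the poloxamer gel into saline will be measured at separate time intervals", with the aim of determining how much drug the gel liberates. Section 3.1 gives the same volumes and times but does not mention the refill. Section 6.2 describes the analysis only in general terms: "In general, data will be summarized using descriptive statistics (mean, median, standard deviation, minimum and maximum" and so on. The Protocol nowhere says that the refill saline contains drug, and nowhere states a correction for drug withdrawn.

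**The concern.** Withdrawing an aliquot from a mixed reservoir does not change its concentration; adding blank saline does. The refill therefore has the opposite effect on concentration to the one claimed for it. What it holds constant is the volume.

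This is more than loose wording. Someone who believes that the concentration is preserved has no reason to account for the drug removed at earlier samples, and would read the second to fourth values as if the tube had been left alone. The size of the error depends on how fast the gel refills the saline, which is the unknown being measured. It can therefore distort the shape of the release curve as well as its level, and no constant factor removes it. Section 3.1 says that the concentration liberated over time is not known, and that values either too low or too high would matter in humans.

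**Working it through.** **Inputs (Protocol 4.2).** Saline volume V = 100 microlitres; aliquot and refill v = 20 microlitres; gel volume G = 1000 microlitres; samples at 0.5, 2, 4 and 168 h, so three refills precede the last sample. The refill is taken as drug-free because the text says only saline.

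**The stated property.** Unchanged concentration means an after/before ratio of 1.00. Mass balance gives

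C_after = C_before × (V − v)/V = C_before × 80/100 = 0.80 × C_before.

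The implied 1.00 is not reproduced.

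**Drug leaving the gel of the sampled tube.** This is what is in the saline now plus what was withdrawn earlier:

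Q_n = 100 × C_n + 20 × (C_1 + … + C_(n−1)), or Q_n/100 = C_n + 0.2 × (sum of earlier readings).

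**Size of the shortfall.** The Protocol gives no kinetics, so the following patterns are assumptions that bracket the effect.

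*Burst before the first sample, nothing afterwards.* Readings are 1, 0.8, 0.8² = 0.64 and 0.8³ = 0.512, while true release stays at 1. Check at sample 4: 0.512 + 0.2 × (1 + 0.8 + 0.64) = 0.512 + 0.488 = 1.000.

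*Constant rate, one unit per hour.* The readings are:
- 0.5 h: 0.5
- 2 h: 0.8 × 0.5 + 1.5 = 1.9, against 2 released (0.95)
- 4 h: 0.8 × 1.9 + 2 = 3.52, against 4 (0.88)
- 168 h: 0.8 × 3.52 + 164 = 166.816, against 168 (0.993)

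*Two-compartment exchange.* The saline concentration moves towards the gel concentration at rate k per hour, with drug conserved between 1000 and 100 microlitres and a partition coefficient of 1.

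*Instant exchange (limit of the above).* The starting level is 1000/1100 = 0.909. Each refill multiplies it by 1 − 20/1100 = 0.982, so the readings are 0.909, 0.893, 0.876 and 0.860. At sample 4, Q_4/100 = 0.860 + 0.2 × (0.909 + 0.893 + 0.876) = 1.396. That is 1.396/0.909 = 1.54 times the first value, although the raw readings fall.

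The results depend on the comparator:

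| Assumed kinetics | Raw ÷ cumulative release, same tube (0.5 h / 2 h / 4 h / 1 wk) | Raw ÷ undisturbed tube |
|---|---|---|
| Burst, then none | 1.00 / 0.80 / 0.64 / 0.51 | same |
| Constant rate | 1.00 / 0.95 / 0.88 / 0.99 | same |
| k = 0.1 | 1.00 / 0.95 / 0.87 / 0.90 | 1.00 / 0.95 / 0.89 / 0.99 |
| k = 1 | 1.00 / 0.91 / 0.79 / 0.68 | 1.00 / 0.98 / 0.96 / 0.96 |
| Instant exchange | 1.00 / 0.83 / 0.71 / 0.62 | 1.00 / 0.98 / 0.96 / 0.95 |

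Against cumulative release, the shortfall across these patterns is 5-20% at 2 h, 12-36% at 4 h and about 1-49% at 1 week. Against an undisturbed, fully re-equilibrated tube it is 1.8%, 3.6% and 5.4%.

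**The correction is not neutral either.** Each withdrawal restores the gradient and draws more drug from the gel. At 1 week, Q_n/100 exceeds the undisturbed reservoir concentration by 41% for k = 1 and by 54% under instant exchange.

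**The case against.** Withdrawing and replacing medium is a legitimate procedure. The correction is a formula that an analysis plan could hold, and both volumes are fixed, so nothing is lost. This stands in part: the data are recoverable, and the replacement itself is not a fault. A reader might infer that the readings will certainly be analysed uncorrected, but the Protocol does not say so. The defect is that it asserts a property that would make a correction unnecessary, and that property is false. A missing formula may be left to an analysis plan; a wrong reason in current text should be corrected where it stands.

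The second objection is that the large figures depend on the comparator and on the kinetics. This stands too. A reader might infer that the test loses about half the signal by 1 week. That needs a burst with no later release, although the gel has ten times the volume of the saline, and nothing in the Protocol supports that pattern. The 38% shortfall under instant exchange is measured against release that the sampling itself provoked. If the quantity wanted is the concentration in 100 microlitres of fluid, which section 3.1 uses to approximate the cochlear volume, the raw reading can be the closer one.

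Third, the consequence is limited. No threshold or go/no-go rule in the Protocol rests on the in-vitro curve, perilymph is measured directly in patients, and section 6.1 calls the study exploratory: "This exploratory study will be used to assess data variability and allow power calculations in future studies". That is fair, and it bears on the weight of the point rather than on its truth.

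Lastly, a reader might infer from the wording about a tube that only one is run per drug, so that the standard deviation in section 6.2 could not be computed. The singular describes one run and does not exclude replicates, and section 6.2 is itself qualified as general. The Protocol does not support that inference.

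**Conclusion.** The point holds in a limited form. The stated reason for the refill is wrong by the Protocol's own volumes: each refill lowers the saline concentration by 20%. This needs only that the refill is drug-free. The 20% is the immediate dilution, not the error in the next reading, because the gel partly refills the saline.

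The direction is certain for cumulative release: every reading after the first falls short of it once some drug has been withdrawn. The size is not certain, and the ranges above are bounds under assumed kinetics, not estimates for these drugs. They also assume a well-mixed reservoir and no loss of drug by degradation or adsorption. The section 3.2 endpoint speaks of rate and liberation, which calls for cumulative release; the concentration question in section 3.1 calls for the reservoir value. These are two different quantities, and the current sentence hides the difference.

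**What to change.** In section 4.2, replace the closing clause on concentrations with a statement that the refill is made to maintain the volume, and say that the refill saline is drug-free.

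For the endpoint of rate or amount liberated, report Q_n = 100 × C_n + 20 × (sum of earlier C_i), with volumes in microlitres. Report the raw reading separately as the reservoir concentration, labelled as diluted by sampling, and do not present Q_n/100 as the concentration in an undisturbed reservoir.

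This is one changed clause and one formula applied to readings already planned, with no extra samples. Optionally, use a separate tube for each time point: this avoids both the dilution and the extra release that sampling provokes, at the cost of more gel per drug.

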5. IN-VIVO STUDY PROCEDURE

5.1 RECRUITMENT

1. Patients who will undergo elective translabyrinthine resection of vestibular schwannoma at Christchurch Hospital or Cochlear Implantation at St George's Hospital will be approached by the surgeon, separate from the surgical consent process.
2. These patients will be given a verbal and written handout of the study procedure and will be consented (See appendix 1)
3. A detailed medical history will be taken during the admission process as well as routine biochemical assessment in order to identify exclusion criteria
4. Eligibility
 - a) Inclusion criteria
 - i. Patients undergoing elective translabyrinthine resection of vestibular schwannoma or
 - ii. Patients undergoing Cochlear Implantation
 - b) Exclusion criteria
 - i. Unstable cardiac disease (Arrhythmias, recent MI/stent)
 - ii. Renal impairment (Creatinine >100 umol/L)

5.2 DETAIL OF PROCEDURE

1. Prepared drug-poloxamer gel solution will be placed in a 1ml syringe with a 22G spinal needle attached
2. After the induction of general anaesthesia the WHO surgical safety checklist will be performed to ensure the correct procedure, site and side.
3. With an operating microscope the drug-poloxamer gel solution will be placed trans-tympanically through the antero-superior portion of the tympanic membrane over the round window.
4. The elective surgical procedure will then proceed as planned with a cortical mastoidectomy, posterior tympanotomy and exposure of the bony labyrinth.
5. Prior to the opening of the inner ear the middle ear will be washed out with 20 mL normal saline to ensure the complete removal of the drug-poloxamer gel.
6. The middle ear will be examined for anatomical variations, such as obstructing mucosal folds over the round window.
7. A micro syringe will then be used to withdraw 20 micro litres of perilymph from the round window

8. Serum for drug levels will be taken at ...
9. The rest of the procedure will then proceed as planned

5.3 MEASUREMENT TOOLS

The perilymph and serum samples will be sent for analysis using the liquid chromatography - tandem mass spectrometry detection method to ascertain the drug concentration

5.4 SAFETY

1. Patients who do not meet the inclusion/exclusion criteria will not be enrolled
2. A WHO surgical safety checklist will be performed to ensure that all members of the theatre team are aware of the planned elective procedure including the possible side effects of the drug-poloxomer gel
3. As part of the routine care of patients undergoing general anaesthesia for resection of vestibular schwannoma there will be constant monitoring of the following
 - i. Heart rate and oxygen saturation
 - ii. Blood pressure through non-invasive blood pressure
 - iii. Cardiac status (Routine 3 lead ECG)

5.4.1 Review and Termination of study

1. If an intra-operative adverse event occurs, that could be attributed to the adenosine ligand (eg. cardiac arrhythmias) an independent committee will be conducted lead by the hospital. If it is deemed that the ligand is the likely cause of the adverse event then the dosing will be reviewed and potential review of further steps surrounding the adverse event that could be implemented to prevent this happening again.
2. If there is no way to further minimise the risk of adverse events to patients the study will be terminated as guided by an independent panel.

6. DATA COLLECTION

The following data will be collected, as completely as possible, for every individual in addition to the liquid chromatography - tandem mass spectrometry detection of perilymph ligand levels

- Demographic data.
 - Age, sex and ethnicity.
- Biochemistry results
 - Preoperative — Creatinine, Liver function tests
 - Intra-operative - Serum levels of adenosine ligands

- Intra-operative adverse events

6. STATISTICAL METHODS

6.1. DETERMINATION OF SAMPLE SIZE

This exploratory study will be used to assess data variability and allow power calculations in future studies.

6.2. STATISTICAL AND ANALYTICAL PLANS

In general, data will be summarized using descriptive statistics (mean, median, standard deviation, minimum and maximum) or frequency counts and percentages, as appropriate to the type of data.

6.3. HANDLING OF MISSING DATA

There will be no imputation for missing data.

7. STUDY DOCUMENTATION

7.1. PROTOCOL AMENDMENTS

No amendments to the protocol may be implemented without prior approval from the Research Office and appropriate Ethics Committee (EC), except when the change involves only logistical or administrative aspects of the study.

7.2. PROTOCOL DEVIATIONS

Serious protocol breaches must be reported according to the local reporting requirements. The nature and reasons for the protocol deviations will be recorded.

8. ETHICS

8.1. ETHICS COMMITTEE AND REGULATORY APPROVAL

The protocol will be submitted for approval to the University of Otago Human Ethics Committee (Health). Prior to study initiation, the investigator will provide the Research Office with a copy of the written Ethics Committee (EC) approval of the protocol. This approval letter will identify the study protocol by protocol title, version, and date. If approval is suspended or terminated by the EC, the investigator will notify the Research Office immediately. It is the responsibility of the investigator to report study progress to the EC as required or at intervals not greater than one year.

8.2. ETHICAL CONDUCT OF THE STUDY

The investigator and all parties involved in this study will conduct the study in adherence to the ethical principles based on the Declaration of Helsinki, ICH GCP guidelines, and applicable national and local laws and regulatory requirements.

9. DATA MANAGEMENT

9.1. DATA COLLECTION

Data will be collected from the following source:

- Health Connect South.

Data will be collected by the named investigators on the front of this application. Collection of data will be limited to information necessary for the specified purposes of the study.

9.2. USE OF DATA

Collected data will be used to answer the research questions described in the protocol.

9.3. FORMS OF DATA

9.3.1. Identifiable Data

Data will be collected in identifiable form. Identifiable data may be accessed by [name], and (if required) the approving IEC.

Data will be collected on a password protected Excel spreadsheets, on a password-protected personal computer. Identifiable data will be retained for at least 10 years.

3.2 De-Identified Data

Identifiable data will be converted to a de-identified form by [name] prior to analysis.

De-identified data will carry a unique subject code only. [name] will retain a log linking subject code with NHI identifier. This log will not be made available to other investigators.

De-identified data will be stored on a password protected Excel spreadsheets, on a password-protected personal computer.

De-identified data may be accessed by study investigators, *if indicated* the consulting statistician, and (if required) the approving EC.

The de-identified dataset (or parts there-of) may be presented in study results, including but not limited to peer-reviewed publications and/or scientific meetings. The de-identified dataset may be made available to other approved researchers on request.

The de-identified dataset will be retained for at least 10 years.

9.4. CONSENT FOR DATA COLLECTION AND USE

A waiver of consent will be requested from the EC approving the study (see Section 8.2.1).

9.5. MĀORI CONSULTATION

Personal and health information is a tāonga and will be treated accordingly.

Formal Māori consultation will be completed as part of the Locality approval process. Any recommendations for additional measures to improve Māori rights and interests in relation to data will be acted upon.

